14.1.1.2. Statistical Analysis Method

- Baseline Patient Demographics

Summary Statistics will be obtained: frequency and percentage will be reported for categorical data; mean, standard deviation, minimum, maximum, median, the 1st and 3rd quartiles will be reported.

- Analysis of the Primary Objective:

All subjects who undergoes an Micra implant procedure will be included in the analysis. The Kaplan-Meier survival analysis will be used to estimate the probability of a subject free from Micra system and/or procedure related major complications. The log-log transformation will be used to calculate the confidence limits.

Definitions:

- Endpoint event for the survival analysis is Micra system and/or procedure related major complications (see 6.2.1)
 - The CEC will finally determine if the adverse event is related to Micra system and/or procedure; and if the adverse event is a major complication
- Censoring occurs in subjects who does not experience any Micra system and/or procedure related major complications
- Follow-up time: from the date of Micra implant procedure to
 - the onset date of a Micra system and/or procedure related major complication, or

Confidential

- study termination date (e.g. subject exit, die, or study closure, etc.), or
- the date of Micra deactivation due to any reason that is not related to the Micra system or procedure (e.g. device system upgrade, the subject's other comorbidities, etc) , or
- the last follow-up date, if none of the above occurs.

- **Analyses of the Secondary Objectives**

The secondary objectives will be analyzed using descriptive statistics. The Statistical Analysis Plan will provide additional details.

- **Safety Evaluation**

All information associated with each adverse event, including event description, severity, and relatedness to the system, etc., will be reported. In addition, event rate will be summarized. The 2-sided 95% Confidence Intervals will be calculated using the Exact Binomial method.

- The statistical analysis of the primary objective will be 2-sided, using 0.05 significance level. The statistical analysis software package SAS will be used to conduct these analysis.

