6.1 Total Enrollment Size

The study will require an enrollment size of 82. The study size is calculated based on statistical hypothesis, assumed expected performance, and projected attrition.

The study pass/fail criteria are based on statistical hypothesis and final analysis results. The analysis of study primary objective will be 6-month success rate comparing to the pre-specified OPC. If the 95% 2-sided confidence interval (CI) lower bound for the probability of freedom from Micra TPS and/or procedure related major complication is greater than 83%, the study will be considered yielding a positive result, demonstrating the success rate is higher than expected values, i.e. study objective will be met.

The study attrition will include all scenarios that result in enrolled subject not being included in the analysis. The common reasons are due to serious protocol deviations (if it affects performance evaluation). Other scenarios may include: Micra implant was not carried out or not successful, follow-up visit not completed per study requirement, or subject withdrawal of consent due to other comorbidities, etc. All these scenarios may constitute subject drop-outs. At the same time, it is assumed that follow-up compliance will be high in pacemaker population. The study attrition is assumed to be 10%.

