6.2 Rationale and Considerations for Sample Size Determination

The study size is determined by the sample size required for the primary objective. Reynolds et al. reported that the Micra TPS and/or procedure related complication free survival probability through 6 months was 96%, (95% CI: 93.3%, 97.6%) in those who underwent Micra TPS implant procedures.³ Therefore, we conservatively assume that the expected performance (or, "Success Rate" in later text) in the study population will be 94%. The OPC is set as 83% (the same performance threshold in the FDA approved global study). The sample size calculation assumes the statistical analysis will be carried out on 0.05 significance level, 2-sided, 80% power and 10% study attrition. The minimum sample size requirement is 82. The sample size formula is displayed as following:

$$n = \frac{[Z_{1-\alpha/2} \sqrt{p_0(1-p_0)} + Z_{1-\beta} \sqrt{p_T(1-p_T)}]^2}{(p_T - p_0)^2};$$

Where p_T is the expected success rate, p_0 is the OPC value, Z value is under normal distribution, α is the type I error (or significance level, 0.05 is used) and β is the type II error (0.2 is used to ensure 80% power).

The sample size calculation employed a formula based on the binomial distribution of the asymptotic normality method because the success rate estimate given by the Kaplan-Meier method is consistent with the actual observed success rate if there are no drop-outs.

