7.9.1.2 Statistical Analysis Method

All subjects who undergo an Micra implant procedure will be included in the analysis. The Kaplan-Meier survival analysis will be used to estimate the probability of a subject free from Micra TPS and/or procedure related relate major complications. The log-log transformation will be used to calculate the 95% confidence limits.

Definitions:

- Endpoint event for the survival analysis is Micra TPS and/or procedure related major complications, defined as those AEs resulting in:
 - Death
 - Permanent loss of device function due to mechanical or electrical dysfunction of the device (e.g. pacing function disabled, leaving device abandoned electrically)
 - System revision (reposition, replacement, explant)
 - Hospitalization
 - Prolonged Hospitalization by 48 hours or more

The CEC will determine if the AE is related to Micra TPS and/or procedure; and if the AE is a major complication. **Note:** Only system or procedure-related AEs will be classified as a major complication, minor complication or an observation. In the event the CEC provides an "Unknown" classification relationship to the Micra TPS and/or procedure, the event will not be considered "Related" for the primary endpoint analysis. Refer to section 7.9.1.4 for additional information.

- Censoring occurs in subjects who do not experience any Micra TPS and/or procedure related major complications
- Follow-up time: from the date of Micra implant procedure to
 - the onset date of a Micra TPS and/or procedure related major complication, or
 - study termination date (e.g. subject exit, die, or study closure, etc.), or
 - the date of Micra deactivation due to any reason that is not related to the Micra TPS or procedure (e.g. device system upgrade, the subject's other comorbidities, etc.), or
 - the last follow-up date, if none of the above occurs.

The statistical analysis of the primary objective will be 2-sided, using 0.05 significance level. The statistical analysis software package SAS will be used to conduct these analyses.

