A Kaplan-Meier survival analysis will be conducted to estimate the freedom from AEs classified as major complications that are related to the Micra TPS and/or procedure by the CEC within 6-months (183 days) post-implant. The Kaplan-Meier method is an appropriate method to analyze this endpoint as it enables inclusion of all subjects with an attempted implant. Additionally, the onset date of all Micra related major complications will be known to the nearest calendar day. Day of follow-up for subjects successfully implanted with the Micra TPS will be calculated as the minimum of the days from successful implant to: (1) onset date of a major complication related to the Micra TPS or procedure (if any), (2) study exit date (if exited), (3) death date (if death occurs), (4) 6-month follow-up visit (if completed), (5) last follow-up visit, or (6) 184 days. Subjects without a major chronic complication related to the Micra TPS and/or procedure during the follow-up period will be considered censored in the Kaplan-Meier analysis. Days of follow-up for subject who have only unsuccessful implant attempt(s) without being successfully implanted will be set to zero (0), unless a major complication occurs in which case the days of follow-up will be calculated from the date of unsuccessful implant attempt to the event onset date. The null hypothesis will be rejected in favor of the alternative if the lower boundary of the two-sided 95% CI is greater than 83%.

The 6-month (183 day) major complication freedom rate will be estimated using the Kaplan-Meier method with the log-log transformation to compute the two-sided CIs, [REDACTED]

[REDACTED]

[REDACTED]

[REDACTED]

Additionally, a corresponding one-sided p-value comparing the 6-month Micra procedure and/or system major complication freedom rate to 83% will be constructed using the formula:

$$z = \frac{\log(-\log(S(t))) - \log(-\log(0.83))}{\sqrt{\sigma(t)^2 / (S(t) * \log(S(t)))^2}}$$

Where $S(t)$ is the observed 6-month (183 days) freedom rate and $\sigma^2(t)$ is Greenwood's estimate of the variance of the survival function at time t . The one-sided p-value will then be computed from the standard normal distribution as $P(Z < z)$ [note this is the area of the standard normal distribution less than z since $\log(-\log(S(t)))$ will be more negative than $\log(-\log(0.83))$ if $S(t) > 0.83$].

[REDACTED]

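### At 82 attempted implants the log-log limit gives up one allowable event compared with an exact limit, and the SAP's additional p-value is wrongly ordered and much too large at 1 to 3 events

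*SAP*

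**What the plan says.** Protocol 14.1.1.2 and SAP 7.9.1.2 estimate freedom from related major complications by Kaplan-Meier and name the same interval. The SAP's wording is "The log-log transformation will be used to calculate the 95% confidence limits"; the Protocol's wording is "The log-log transformation will be used to calculate the confidence limits". The pass rule (Protocol 14.1.1.1 and 14.1.5; SAP 6.1, 7.9.1.1 and 7.9.1.2) is a lower limit of the two-sided 95% interval above 83%.

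On the level, the SAP says: "The statistical analysis of the primary objective will be 2-sided, using 0.05 significance level". That leaves 2.5% on the deciding side.

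SAP 7.9.1.2 then adds a second quantity: "a corresponding one-sided p-value comparing the 6-month Micra procedure and/or system major complication freedom rate to 83% will be constructed using the formula". The formula is a z statistic on the log(-log) scale with Greenwood's variance. The visible text gives no one-sided benchmark for it.

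On size, SAP 6.1 says "The study will require an enrollment size of 82", and SAP 6.2 assumes a 94% freedom rate. The primary set is every subject with an attempted implant (SAP 7.9.1.3). Some text next to the interval and the p-value formula is redacted.

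**The concern.** The log-log limit is a normal approximation with an estimated variance, applied to about 82 subjects with a handful of events. Two things could go wrong.

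The deciding limit could lie low enough to fail a result that a valid 2.5% test would accept. That would matter in a registration trial whose expected result is only a few events from the boundary.

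The p-value could also misstate the evidence when complications are rare, because the estimated standard error on the log(-log) scale grows quickly as events approach zero. It is one-sided, but the only level stated for this analysis is 0.05 two-sided. A printed value between 0.025 and 0.05 could therefore be read as significant although the objective has failed.

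**Working it through.** **Inputs.** Null rate 0.83, expected rate 0.94, two-sided level 0.05, power 80%, attrition 10% (SAP 6.2); enrolment 82 (SAP 6.1); log-log limit, Greenwood variance and z formula (SAP 7.9.1.2).

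**The plan's own figure.** [1.960·√(0.83·0.17) + 0.8416·√(0.94·0.06)]² / 0.11² = (0.7362 + 0.1999)² / 0.0121 = 72.4, rounded up to 73; 73/0.9 = 81.1, rounded up to 82. The stated size reproduces. The formula is a binomial normal approximation with the null variance at 83%, not the log-log method.

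**Formulas, with nobody censored before day 183.** With d events in n subjects:
- S = 1 − d/n, and se = √(d/(n(n−d))) / |log S| on the log(-log) scale.
- Log-log lower limit = exp(−exp(log(−log S) + 1.96·se)).
- z = (log(−log S) − log(−log 0.83)) / se, and p = P(Z < z).
- Exact lower limit = the 0.025 quantile of Beta(n−d, d+1). Exact p = P(X ≤ d) for X binomial(n, 0.17).

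Example, d = 7, n = 82: S = 0.9146, log(−log S) = −2.4165, se = 0.3781. The limit is exp(−exp(−2.4165 + 0.7410)) = 0.8293, a fail. z = (−2.4165 + 1.6802)/0.3781 = −1.947, so p = 0.0257.

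**Results at n = 82.**

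| Events | Log-log limit | Exact limit | SAP p | Exact p |
|---|---|---|---|---|
| 1 | 91.7% | 93.4% | 0.0033 | 0.000004 |
| 2 | 90.6% | 91.5% | 0.0021 | 0.00004 |
| 3 | 89.1% | 89.7% | 0.0027 | 0.0002 |
| 4 | 87.5% | 88.0% | 0.0043 | 0.0009 |
| 5 | 86.0% | 86.3% | 0.0076 | 0.0032 |
| 6 | 84.4% | 84.8% | 0.0140 | 0.0092 |
| 7 | 82.9% | 83.2% | 0.0257 | 0.0225 |
| 8 | 81.4% | 81.7% | 0.0460 | 0.0480 |

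**Deciding limit.** Log-log passes up to 6 events: P(X ≤ 6) is 0.92% at a true event rate of 17% and 77.9% at 6%. The exact limit passes up to 7: 2.25% and 88.1%. The difference is the case of exactly 7 events, which has probability 10.3% at a true rate of 94%.

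**Other sizes, no censoring.** For n from 70 to 92 the two rules are identical at 19 of 23 sizes. They differ, by one event each time, at 74, 81, 82 and 89. Log-log error is 2.04% at n = 75, 2.02% at 83 and 2.19% at 90. The exact rule moves up and down in the same way: 0.99% at 73, 1.16% at 80.

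**Early censoring.** Simulation with 82 attempts and 12,000 runs per cell. It assumes 1% failed attempts, 70% of events on days 0–1 and random early censoring. The comparator is the beta-product limit.

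| Censored early | Error, log-log / beta-product | Passing at 94%, log-log / beta-product |
|---|---|---|
| 3% | 0.9% / 1.6% | 78.5% / 83.4% |
| 5% | 1.0% / 1.6% | 78.7% / 81.8% |
| 10% | 0.9% / 1.0% | 79.4% / 80.0% |

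The gain in passing is 4.9, 3.1 and 0.6 points. The beta-product error stayed at or below 2.3% throughout.

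**p-value.** From 2 events to 1, the numerator of z goes from −2.021 to −2.720, a factor of 1.35. The standard error goes from 0.707 to 1.000, a factor of 1.41. So z moves towards zero (−2.858 to −2.720) and p rises. The ratio of SAP p to exact p is about 800, 59 and 12.5 at 1, 2 and 3 events, and 4.6 and 2.4 at 4 and 5. One to three events has probability 26% at a true rate of 94%, and 55% at the 96% reported from the global study.

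**The case against.** The strongest reply is that this is mostly binomial discreteness. A reader might infer that the method has a real error of 0.9% instead of 2.5%. The figures do not support that: one more subject takes log-log error to 2.02%, and the exact rule has the same ups and downs. Nor do few events explain the 0.92%. It is set at the 6/7 boundary, where the two limits differ by only 0.3 to 0.4 points, and under the null about 14 events are expected (82 × 0.17 = 13.9). This stands. But at 82 both methods face the same discreteness, and only log-log loses the event.

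A second reply is that 10% attrition leaves about 73 subjects, where the rules coincide (5 events, error 0.99%, chance of passing 72.7%). This stands in part. Subjects never attempted drop out of the primary set, and event-free failed attempts are censored at day 0. But subjects who exit later keep their data up to censoring (SAP 7.4, 7.9.1.4), so the number at risk can start near 82. The shrinking gain in the simulation is the fair measure.

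Third, the p-value decides nothing. The limit alone is the pass rule, z below −1.96 is algebraically the same condition, the limit rises steadily as events fall, and 1 to 6 events all pass. This stands in full. The SAP also already labels the p-value one-sided; only the 0.025 benchmark is missing from the visible text, and redacted text may contain it.

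**Conclusion.** Two modest points hold.

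First, at 82 attempted implants without early censoring, the planned limit allows one event fewer than a valid exact limit. This costs about 10 points of passing at the plan's own 94% (77.9% against 88.1%). The loss is specific to a few sample sizes and shrinks to under 1 point at 10% early censoring. It is conservative, so it adds no risk of a false pass. At every n from 70 to 92 the exact rule allows as many events or one more, with error at or below 2.5%.

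Second, the additional p-value is wrongly ordered at 1 to 3 events and tenfold or more too large there, and about 2 to 5 fold too large at 4 to 5. At 7 or 8 events it prints 0.026 or 0.046 although the objective fails. The assumed 94% implies about 5 events (82 × 0.06 = 4.9), so it would be too strong to say that the tenfold distortion covers the whole expected range.

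These results assume that zero events counts as a pass; the log-log formula is undefined there, and redacted text may deal with it. The censored figures rest on the simulation's assumptions about event timing and random drop-out.

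**What to change.** Before any outcome is tabulated:

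- In SAP 7.9.1.2, replace the z formula by an exact-type p-value: exact binomial if nobody is censored before day 183, beta-product otherwise. State that it is judged at one-sided 0.025.
- By CIP amendment to Protocol 14.1.1.2, with matching SAP text, make the lower 97.5% beta-product limit for 183-day freedom the deciding limit. It equals Clopper-Pearson when there is no early censoring. Keep the log-log limit as supportive. SAP 7.12 requires an amendment when a principal feature changes, and the pass rule is one.
- State the one-sided error and the chance of passing across plausible numbers of attempts and censoring rates.

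Switching to a logit transform is not a cure. At n = 82 its p-values are 0.0026, 0.0017 and 0.0021 at 1, 2 and 3 events, the same disorder, and at n = 81 it still passes only 6 events.

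The cost is wording, one validated program and a less familiar interval to explain to the regulator. No patients are added. If the sponsor prefers to keep the log-log rule, the p-value replacement and the operating characteristics are still worth making on their own.

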10.1.3.1. Unsuccessful Implant Detail

If a Micra device is not successfully implanted, subjects will be exited from the study within 30-days post the date of implant procedure unless a study system and/or implant procedure related Adverse Event (AE) is identified. If a study system and/or implant procedure related AE is identified, the subject will be followed until the event is resolved or no further actions need to be taken.

Confidential

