7.7.1 Implant

Implant information will be collected on eCRFs for all enrolled subjects. For subjects with successful implants, variables to be summarized include, but are not limited to: device location, number of times engaged, anticoagulation, type of anesthesia, closure method, impedance, R-Wave measurement, auto decrement threshold, capture management threshold, and procedure durations (e.g. skin to skin, introducer in/out, etc.). Summary statistics will be obtained: frequency and percentage will be reported for categorical data; mean, standard deviation, minimum, maximum, median, the 1st and 3rd quartiles will be reported for continuous data.

For subjects with unsuccessful implant attempt, a listing will be compiled to summarize available information, including the reason(s) the implant attempt was unsuccessful.

The Micra implant success rate will be assessed on a per subject basis, calculated as the number of subjects successfully implanted with a Micra TPS divided by the total number of subjects with at least one implant attempt expressed as a percentage.

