7.9.1.3 Determination of Subjects for Analysis

The primary objective will be analyzed using the FAS. All subjects with an attempted implant of the Micra TPS will be included in the analysis.

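### SAP 7.9.1.2 defines follow-up for the primary endpoint in two conflicting ways, and the second misplaces a complication at a failed attempt that precedes a later success and discards event-free time after failed implants

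*SAP*

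**What the plan says.** **Population.** SAP 7.9.1.3 states: "All subjects with an attempted implant of the Micra TPS will be included in the analysis". SAP 7.9.1.2 says the same and gives this inclusiveness as a reason for using Kaplan-Meier.

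**First definition of follow-up.** The bulleted definitions in SAP 7.9.1.2, like Protocol 14.1.1.2, start follow-up at the date of the Micra implant procedure. It ends at a related major complication, study exit, death or closure, an unrelated deactivation, or otherwise the last follow-up.

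**Second definition of follow-up.** Later in SAP 7.9.1.2: "Day of follow-up for subjects successfully implanted with the Micra TPS will be calculated as the minimum of the days from successful implant to" six listed times, among them onset of a related major complication and a cap of 184 days. No lower limit is given. For subjects without a device: "Days of follow-up for subject who have only unsuccessful implant attempt(s) without being successfully implanted will be set to zero (0"). The exception is a subject with a major complication, whose time is counted from the failed attempt to onset.

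**Repeat attempts.** The second definition refers to subjects with only unsuccessful attempts, in an optional plural. SAP 7.7.1 bases the implant success rate on "the total number of subjects with at least one implant attempt expressed as a percentage".

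**Exit after a failed implant.** Protocol 10.1.3.1: "subjects will be exited from the study within 30-days post the date of implant procedure unless" a related adverse event is identified. Such a subject is followed until the event resolves or needs no further action.

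**Use of data before exit.** Protocol 10.6 and SAP 7.4 both say that data gathered before exit enter the analysis.

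**The concern.** The two definitions agree for a subject implanted successfully on the first procedure date. They differ for two kinds of subject.

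1. *Failed attempt, then success on a later date.* This subject ends up implanted, so the second definition counts from the successful implant. A major complication at the earlier attempt has its onset before that date, and the minimum rule selects the negative number. Kaplan-Meier has no place for it. The attempt-date clock does not help, because it is reserved for subjects who never receive a device.

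2. *Attempted, never implanted, event-free.* The first definition credits time up to exit. The second credits none, whatever was observed. The subject is counted as included but is at risk on day 0 only. SAP 7.9.1.4 discusses missing data only for successfully implanted subjects who discontinue, so this group has no stated treatment.

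The endpoint concerns procedure and system safety and decides pass or fail. If the timing rule is left to be settled once the events are known, a known event could be placed, moved or dropped by choice.

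**Working it through.** **Inputs.** From SAP 6.2: "The sample size calculation assumes the statistical analysis will be carried out on 0.05 significance level, 2-sided, 80% power and 10% study attrition"; the expected freedom rate "in the study population will be 94"%; "The OPC is set as 83"%. The rule in SAP 7.9.1.1 and 7.9.1.2 passes if the lower limit of the two-sided 95% log-log Kaplan-Meier interval exceeds 83%. Global study (Protocol 6.2.1): 725 subjects attempted, 719 implanted.

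**Step 1. Reproduce the sample size.**
n = [1.960 × √(0.83 × 0.17) + 0.842 × √(0.94 × 0.06)]² / 0.11² = (0.7362 + 0.1999)² / 0.0121 = 72.4, rounded up to 73. Then 73 / 0.9 = 81.1, rounded up to 82. This matches the plan.

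**Step 2. Lower limits for d events in n subjects.** With complete follow-up and all events on day 0, S = 1 − d/n and the Greenwood sum is G = d/[n(n − d)]. The limit is exp{−exp[log(−log S) + 1.960 × √G/|log S|]}.

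For 7 of 82: S = 0.9146, G = 0.001138, log(−log S) = −2.4165, √G/|log S| = 0.3781, limit 0.8293.

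| True events in 82 | Limit, all counted | Limit, one record lost (n = 81) | Decision |
|---|---|---|---|
| 6 | 84.4% | 85.8% | pass either way |
| 7 | 82.9% | 84.3% | fail becomes pass |
| 8 | 81.4% | 82.7% | fail either way |

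A lost record therefore matters only at exactly 7 true events. Under a binomial with n = 82, that count has probability 10% at a freedom rate of 94% and 3% at 96%. The chance of a reversal is smaller still, because one of the 7 must also be a complication at a failed attempt followed by success on a later date.

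**Step 3. Zero-day censoring.** If every event is on day 0, nothing changes, because zero-day subjects are still at risk that day. If 6 events occur later (day 20 assumed), the zero-day subjects have left the risk set:

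| Zero-day subjects | Lower limit |
|---|---|
| 0 | 84.4% |
| 1 | 84.3% |
| 2 | 84.1% |
| 4 | 83.7% |
| 8 | 82.8% |

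Crediting those subjects with 30 event-free days restores 84.4%.

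**Step 4. How many never-implanted subjects to expect.** 725 − 719 = 6, so the rate is 6/725 = 0.83%. Expected in 82: 82 × 6/725 = 0.68. Chance of at least one: 1 − (719/725)^82 = 49%; of at least two, 15%. These figures describe subjects left without a device. They do not describe the failed-then-successful group, whose frequency the documents do not give.

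**The case against.** The strongest reply is that the intent is clear and the problem case is remote. SAP 7.1.4 item (5) keeps in the primary analysis a subject who has an endpoint failure during an unsuccessful attempt. The first definition of follow-up already starts at the procedure. No section describes a second attempt on another date, and Protocol 10.1.3.1 and 10.6 treat a failed implant as grounds for exit. Data cleaning and independent programming of the primary analysis (SAP section 8) would probably catch a negative time.

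Most of this stands, and it limits the point without removing it. Item (5) shows that events at failed attempts are meant to count, but it is written for subjects who end without the study device. The first definition does not say which procedure date applies when there are two. Programmers checking each other's work would still have to choose between two written rules.

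Three stronger readings are tempting and not supported:

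- *That both rules favour the device.* A lost event would. The zero-day rule alone leaves the lower limit unchanged or lowers it slightly.
- *That software will silently drop the record.* The documents do not say how a negative time would be handled. Loss of the record in Step 2 is an assumption.
- *That early exit hides late complications.* Protocol Table 1 lists fistula, deep vein thrombosis and effusion, but gives no onset times and no split by implant success. An event after exit would not be recorded, but the documents do not allow its likelihood to be sized.

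There is also a fair objection to the remedy. The endpoint is worded as 183 days post-implant, so starting at the first attempt shortens the post-implant window for a re-attempted subject. With an assumed 20-day gap, day 183 from the first attempt is post-implant day 163. The fix has to deal with this.

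**Conclusion.** The point holds as an internal conflict with an uncovered case. SAP 7.9.1.2 contains two follow-up definitions that cannot both be applied to subjects with a failed attempt. The second conflicts with Protocol 14.1.1.2 on the time origin, and with Protocol 10.6 and SAP 7.4 on the use of data before exit.

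The numerical consequence is small. A mishandled event reverses the decision only at 7 true events in 82, assuming complete follow-up, day-0 events and loss of the record. It also needs a rare chain of unstated frequency. The zero-day rule moves the limit by about 0.2 points per affected subject, against the device, with 6 later events; fewer than one such subject is expected at the global rate. The sample size of 82 is unaffected. The change is still worth making, because these rules time the pass/fail endpoint and can be settled in advance at almost no cost.

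**What to change.** 1. In Protocol 14.1.1.2 and both parts of SAP 7.9.1.2, use one time origin for every attempted subject: the date of the first Micra implant attempt, whether or not a later attempt succeeds.
2. Count from that date any major complication that the Clinical Events Committee judges related to the system or procedure.
3. State that the 183-day window runs from the same origin, or report the post-implant window as a sensitivity analysis.
4. Replace the zero-day rule with censoring at exit or last contact.
5. Extend SAP 7.9.1.4 to cover attempted subjects who are never implanted.
6. Reconcile the exit timing in Protocol 10.1.3.1 with the analysis of all attempted subjects in SAP 7.9.1.2 and 7.9.1.3.

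The cost is minor wording in the SAP and the matching protocol text. No subjects are added. The only analytic downside is a small shift of the window for any re-attempted subject, which item 3 addresses.

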4.1 Primary Objective

To demonstrate the Micra TPS is safe by estimating the Micra TPS implant procedure and/or system related major complications free survival probability through 6 months post implant.

The study primary endpoint is defined as a subject's first occurrence of a major complication related to the Micra TPS and/or Micra procedure as determined by the Clinical Events Committee (CEC) that occurs on or prior to 6-months (183 days) post-implant.

Major complications are those Adverse Events (AEs) resulting in:

- Death
- Permanent loss of device function due to mechanical or electrical dysfunction of the device (e.g. pacing function disabled, leaving device abandoned electrically)
- System revision (reposition, replacement, explant)
- Hospitalization
- Prolonged Hospitalization by 48 hours or more

Note: Only system or procedure-related AEs will be classified as a major complication, minor complication or an observation.

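### SAP 7.9.1.2 gives two follow-up rules for the primary endpoint that do not agree; read literally, one censors a known related major complication that starts after the last visit

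*SAP*

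**What the plan says.** The endpoint in SAP 4.1 is the first related major complication, as determined by the CEC, "that occurs on or prior to 6-months (183 days) post-implant". The objective is met if the lower limit of the two-sided 95% log-log Kaplan-Meier interval exceeds 83%.

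SAP 7.9.1.2 then states follow-up and censoring twice.

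- **Definitions list** (the same structure as Protocol 14.1.1.2). The clock is defined by "Follow-up time: from the date of Micra implant procedure to" one of several end dates: event onset, study termination, unrelated deactivation, or "the last follow-up date, if none of the above occurs". On status: "Censoring occurs in subjects who do not experience any Micra TPS and/or procedure related major complications".
- **Day-count paragraph**, for successfully implanted subjects. Follow-up "will be calculated as the minimum of the days from successful implant to: (1) onset date of a major complication", then study exit, and the list closes with "3) death date (if death occurs), (4) 6-month follow-up visit (if completed), (5) last follow-up visit, or (6) 184 days". On status: "Subjects without a major chronic complication related to the Micra TPS and/or procedure during the follow-up period will be considered censored".

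The visible text does not say which statement governs.

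**The concern.** In the definitions list, a known event takes precedence over the last visit. In the day-count paragraph, the last visit is an unconditional member of a minimum, so it can come before the event. If status is then judged within that shortened time, an adjudicated event by day 183 becomes a censored observation. This contradicts SAP 4.1 and raises the complication-free estimate in a single-arm safety test.

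The wording can be reached in two ways:

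- A related major complication starts after the last follow-up visit. The clear example is a related death after a first follow-up visit. Explant followed by exit is only a possible example, because Protocol 10.1.5 delays exit until related events are resolved or no further action will be taken.
- The 6-month visit is held before day 183, which SAP 7.1.4 item (4) foresees, and the event falls between that visit and day 183.

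Two programmers working independently, as SAP Section 8 requires for this analysis, could implement different rules from the same section and reach different pass/fail results.

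**Working it through.** **The two statements side by side**

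| Feature | Definitions list | Day-count paragraph |
|---|---|---|
| Last visit | Only if nothing else applies | Always in the minimum |
| 6-month visit | Not listed | In the minimum if completed |
| Who is censored | No related major complication | No *chronic* related major complication in the follow-up period |
| Unrelated deactivation | Ends follow-up: "the date of Micra deactivation due to any reason that is not related to the Micra TPS or procedure" | Not listed |
| Time origin | Implant procedure | Successful implant |
| Event-free subject who exits or dies after the last visit | Exit or death date | Last visit, since it is the earlier date |

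The endpoint definition has no *chronic* qualifier. *Follow-up period* is not tied to the computed day count; SAP 5.1 uses a similar phrase for the whole study.

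**One subject.** Assume a last visit on day 90 and a related major complication on day 120. The definitions list gives an event at day 120. The day-count paragraph gives min(120, 90, 184) = 90. Read literally, the subject is censored at day 90. If status is taken from the definitions list, the subject is an event dated day 90.

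**The plan's own figure.** With p0 = 0.83, pT = 0.94, two-sided 0.05 and 80% power (SAP 6.2), the formula gives n = 72.42, rounded up to 73. Then 73/0.90 = 81.1, rounded up to 82, as stated. The point does not change the sample size.

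**Effect on the lower limit.** Event-free subjects are censored at day 184. With d failures at one time among n at risk:

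- S = (n − d)/n
- Greenwood sum G = d/[n(n − d)]
- s = √G/|ln S|
- Lower limit = S^exp(1.96 s)

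For n = 82, d = 7, all counted: S = 75/82 = 0.9146, G = 7/(82 × 75) = 0.001138, s = 0.3781, lower limit **0.8293, fail**.

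One of the seven censored at an earlier visit:

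- The other six fail before that visit: S = 76/82 = 0.9268, s = 0.4083, lower limit **0.8444, pass**.
- The other six fail after that visit, with 81 at risk: S = 75/81 = 0.9259, s = 0.4083, lower limit **0.8425, pass**.

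The same event counted but dated early gives 0.8293 in every case computed (onset day 50, 60 or 150 with last visit day 30, 30 or 90; onset day 182 after a 6-month visit on day 175).

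| n | Failures | All counted, or counted but dated early | One censored (literal reading) |
|---|---|---|---|
| 82 | 7 | 0.8293, fail | 0.8425 to 0.8444, pass |
| 74 (82 less 10%) | 6 | 0.8284, fail | 0.8432 to 0.8453, pass |
| 73 | 6 | 0.8262, fail | 0.8412 to 0.8432, pass |

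**Chance of passing at n = 82.** The pass limit is 6 counted failures. Failures are taken as binomial, with no other early censoring. The documents do not give the share of events that would be lost, so it is assumed, with each event lost independently.

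| True rate | None lost | 2% | 5% | 10% |
|---|---|---|---|---|
| 83% | 0.9% | 1.1% | 1.5% | 2.4% |
| 90% | 27.6% | 29.6% | 32.8% | 38.6% |
| 94% | 77.9% | 79.3% | 81.4% | 84.6% |

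If exactly one event were always lost, the chance at a true 83% would be P(X ≤ 7) = 2.2% with n = 82, and P(X ≤ 6) = 2.5% (0.0254) with n = 73, where the pass limit is 5. A 20% loss at n = 82 would give 5.9%, but nothing in the documents suggests a share that large.

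**The case against.** The strongest reply is that event status is already settled. The definitions list censors only subjects with no related major complication. The day-count paragraph itself opens by estimating freedom from such events within 183 days and says that their onset dates will be known. SAP 7.1.4 item (3) keeps a subject who fails and is then lost. On this view the minimum defines only a time variable, the event is counted, and the limit stays at 0.8293. As a statement of intent this stands. It does not fully settle the text, because the same paragraph has its own, differently worded censoring sentence, and the minimum would still misdate the event.

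Secondly, the last follow-up visit may include the unscheduled visit at which the event was found. SAP 7.9.2.2 refers to unscheduled visits, and SAP 7.9.2.1 says scheduled when it means scheduled. On that reading most of the problem goes, but the SAP does not define the term this way.

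Thirdly, the reach is narrow. Any subject with a visit on or after onset, including an in-window 6-month visit, is unaffected unless an earlier 6-month visit fell before onset. This stands and limits the weight of the point.

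Parts of SAP 7.9.1.2 are blacked out, so the point is confined to the visible text.

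A reader might go further in two ways that the documents do not support:

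- **That the plan sets out to drop or hide late complications.** SAP 4.1, SAP 7.1.4 item (3) and the paragraph's own opening point the other way, and the events would still appear in the adverse event and death tables.
- **That the deactivation difference has a known effect on the verdict, because the definitions list would drop a related event after an unrelated deactivation.** That requires its list of end dates to override its own censoring statement, which covers only subjects with no related event. The difference should be reconciled, but no numerical effect is claimed for it.

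**Conclusion.** The point holds as a minor wording correction to the rule for the primary endpoint. The two statements in SAP 7.9.1.2 differ, and the day-count paragraph, read literally, can censor an event that SAP 4.1 counts. On that reading a single subject can change the verdict at the margin (82.9% against 84.2% to 84.4% with 82 subjects and 7 failures). On the reading that best fits the plan's intent, the lower limit does not change in the cases computed.

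Few subjects are likely to be affected, although the documents give no number. At a true rate of 83% and n = 82, the chance of passing stays below the nominal one-sided 2.5% for losses up to 10% of events. The larger shifts, at true rates of 90% and 94%, concern a device that does exceed 83%. The figures rest on the assumed visit and onset days, the binomial model and the assumed loss range. The reason to act is that the pass/fail rule should have one meaning before the data are locked.

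**What to change.** In the day-count paragraph of SAP 7.9.1.2, before database lock:

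1. Assign event status first, for example: *Any subject with a CEC-adjudicated related major complication on or before day 183 is an event at its onset date, regardless of visit dates.*
2. Apply items (2) to (6) of the minimum only to subjects without such an event.
3. Delete *chronic* from the censoring sentence.
4. Make the definitions list and the day-count paragraph state the same time origin, the same treatment of unrelated deactivation, and the same censoring date for event-free subjects, including those who exit or die after their last visit.
5. Keep the existing rule for subjects who have only unsuccessful implant attempts.

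The cost is one paragraph of SAP wording. It needs no new data, adds no burden for subjects and leaves the sample size at 82.
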